Section 5.4.2 Potential Risks of Premedication; Section 7.1 Study Design; Section 7.1.4 Dose Rationale; Section 8.3.2 Subject-level Redosing and Stopping Criteria; Section 9.1.1 Premedications; Section 9.1.3 Clinical Observation and Supportive Care; Section 9.5 Rescue Medications	The sentence “If dexamethasone (or equivalent) is used as a rescue medication, premedication with dexamethasone (or equivalent) should be considered for all subjects’ subsequent infusions” was updated to “If dexamethasone (or equivalent) is used as a rescue medication, premedication with dexamethasone (or equivalent) should be considered for that subject’s subsequent infusions after discussion with the Medical Monitor.” Similar edits were made in sections that referenced this guidance.	Subjects may have different sensitivities, requiring an individualized assessment for the use of additional premedication.
Schedule of Events Table 4 and Table 6; Section 10.4.3.1 Creatine Kinase and Myoglobin Section 10.4.3.2; Calf Magnetic Resonance Spectroscopy; Section 10.5.3 Serum Biotinidase; Appendix 3	Serum myoglobin, serum biotinidase, and calf MRS were removed from the study for all cohorts.	To reduce subject burden, assessments for these exploratory PD endpoints were removed.
Schedule of Events Table 6	The Week 12, 24, and 36 Visits for DB-RD cohorts were changed to be conducted at home. As a result, Fibroscan or ultrasound elastography will be conducted at Week 10 instead of Week 12; and GNEM-FAS, Patient-reported Outcomes Measurement Information System (PROMIS), and handheld dynamometry (HHD) will be assessed at Week 10, and not at Weeks 12, 24, and 36.	To reduce subject burden.
Appendix 5	Text regarding Data Protection, Anonymization, and Security in Appendix 5, was updated to reflect the latest regulatory guidance.	Updated per regulatory guidance and for clarity.

Section # and Name	Description of Change	Brief Rationale
Section 5.5 Risk Minimization	Text regarding the collection of safety labs in Section 5.5 Risk Minimization was updated to align with the schedule of events.	To correct and align protocol text with the schedule of events.

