^f Refer to [Table 8](#) for details of PK sampling. Please note that sample collections are marked for W1, W2, W9, W10, and W12 in this table ([Table 6](#)) corresponding to a sample collection 7, 14, and 28 days after infusion of UX053 on W0 and/or W8 as outlined in the final rows of the first column in [Table 8](#); a 28-day post infusion collection is only collected for the W8 assessment for DB-RD cohorts. PK samples are also collected 24-hours post infusion as noted in [Table 8](#).

^g Sample to be collected pre-dose and at the end of the infusion. Post-infusion blood samples should be collected in the opposite arm of the infusion to avoid dilution.

^h Optional safety assessments to be performed (and repeated as necessary) at the discretion of the Investigator if nutrition changes are made during screening.

ⁱ Close monitoring is required for subjects who develop elevations in ALT > 3x ULN and > 2x their baseline value, or elevation in ALT > 3x ULN with INR > 1.5. This includes repeating liver enzymes and INR within 48 hours and consideration of additional diagnostic tests such as liver ultrasound ([Section 10.1.5](#)).

^j All efforts should be made for urine collections to be consistently taken from the first morning void.

^k All imaging assessments (liver MRI, liver MRS, and Fibroscan or ultrasound elastography) can be conducted at any time during screening or within 1 week prior to the corresponding visit. Liver MRS are only required at sites with capability. Scanning for liver MRS can be conducted immediately following the liver MRI. If feasible, glycoNOE imaging of the liver, may be collected at the time of the liver MRI.

^l A 3- to 4-hour fasting period is preferred, but not required, prior to blood collection for serum HDL and LDL. All efforts should be made to obtain samples for HDL and LDL consistently for a given subject.

^m Nutrition diary recordings should be recorded at least 3 consecutive days per week through Screening and for the 3 consecutive days in the week leading up to each subsequent visit. Qualified Investigator site staff should review nutrition diary data at each visit.

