with a HHG that will be provided by Ultragenyx at ISV. When CGM data is being collected, all subjects will connect their CGM and HHG devices to a study-provided laptop weekly and upload CGM and HHG data. At remote visits, in conjunction with assessments performed by a home health nurse, the site will contact subjects by telephone or videoconference to confirm the CGM device is properly in use and data was uploaded; answer any questions regarding or help troubleshoot (if necessary) CGM device use; and review CGM data, HHG data (when applicable), and nutrition diary entries; outside of scheduled visits, these telephone calls will occur as needed. At in-clinic visits, a conversation between the site and the subject should occur to ensure CGM compliance and troubleshoot if needed.

^q RBC, WBC, serum and plasma samples will be collected for future biomarker assessments yet to be determined.

Note: White columns indicate in-clinic visits (ISV, STV, BL/W0, W2, W4, W6, W8, W10, and EOS III W48/ET). Gray columns indicate visits conducted at home (NOV, W1, W3, W5, W7, W9, W12, W24, and W36). A telephone call is required if NOVs occur, but not for W1 and W9. A visit from a home health nurse is required for W1, W3, W5, W7, W9, W12, W24, and W36, but may not be necessary for NOVs.

Note: Laboratory assessments included in chemistry, hematology, and urinalysis are provided in [Appendix 3](#).

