5.4.1.1. Potential Risks Identified from Nonclinical Studies

A review of nonclinical studies with UX053 informed the identification of the following potential risks for UX053: hypersensitivity, hepatotoxicity, and consumptive coagulopathy.

Summaries of nonclinical studies with UX053 are provided in the IB. Across species (mouse, rat, dog, and monkey), the key potential risks identified in nonclinical studies were hypersensitivity, consumptive coagulopathy, and hepatotoxicity. The potential risks are likely triggered in part by immune system activation including, complement activation and cytokine release. Clinical signs of complement activation can include fever, tachycardia, hypotension, body aches, nausea and vomiting, rash, and edema.

ADAs to human GDE and CCI [REDACTED] developed in rats, dogs, and monkeys after repeat administration of UX053. Increasing titers over time coincided with a progressively higher magnitude induction of cytokines and complement activation at later doses in dogs and monkeys (cytokines and complement not measured in rats). The presence of CCI [REDACTED] ADAs did not have an impact on UX053 mRNA and ATX95 exposure in these studies.

Hepatotoxicity was identified by increases in transaminases and corresponding changes in histopathology. At lower doses, rises in transaminases were transient and reversible. Importantly, these changes are clinically monitorable.

In the nonclinical toxicology studies in rat and cynomolgus monkey, toxicity was observed at doses of CCI [REDACTED] higher than the highest potential dose assigned in this FIH study on a mg/kg basis. Dogs, which have been reported as a model with hypersensitivity to nanoparticle formulations (Szebeni et al., 2018; Szebeni et al., 2007), had symptoms of toxicity at CCI mg/kg UX053, which is higher than the highest potential dose in this FIH study (option to dose up to CCI mg/kg). The heightened sensitivity to such reactions in dogs may translate to similar types of findings in patients who experience hypersensitivity (eg, IRRs), and hypersensitivity has been identified as an important potential risk and will be carefully monitored. Toxicology findings from UX053 nonclinical studies across species were consistent with findings for other siRNA or mRNA LNP therapies (Levin, 2019; Sabnis et al., 2018; Sedic et al., 2018; Henry et al., 2016).

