5.5. Risk Minimization

Several components of this FIH study are designed to mitigate the potential risks of study participation, including implementation of a DMC, 72-hour intervals between dosing of individual subjects within a given SAD cohort, a cautious dose escalation scheme, slow drug infusion rate, prespecified premedications, availability of rescue medications, continuous cardiorespiratory monitoring during infusions, and 24-hour observation post infusion to monitor for post infusion effects.

Dose escalation will occur only after safety data reviews by the DMC. The DMC consists of a panel of independent medical and scientific experts (Section 7.1 and Section 11.12). Standard

safety laboratory tests are collected immediately prior to dosing (all cohorts) and again approximately 24 hours after dosing and at Day 4 (SAD cohorts) and Day 7 (both SAD and RD cohorts) (Section 10.1.5). In addition, characterization of complement activation through classical and alternative pathways, cytokine release, fibrinogen, and d-dimer will be assessed predose and at the end of each infusion. Potential risks of UX053 treatment identified from available nonclinical data with UX053 and known risks associated with siRNA or mRNA LNP therapies (Section 5.4.1) will be monitored throughout participation in the SAD and RD cohorts. Subjects will be monitored in an inpatient or observational unit for 24 hours after the end of each infusion.

The starting dose of UX053, 0.05 mg/kg, is approximately CCI below the human equivalent dose (HED) for the no-observed adverse effect level (NOAEL) for repeat dosing in dogs, approximately CCI below the HED for the NOAEL for repeat dosing in rats, and approximately CCI below the HED for the NOAEL for repeat dosing in cynomolgus monkeys using CCI scaling to calculate HED. The relative dose increase becomes smaller with each subsequent cohort: after a CCI dose increase from Cohorts 1S to 2S to 3S, there is a CCI dose increase between cohorts 3S and 4S. For RD cohorts, sequential doses may be reduced for individual subjects or for entire cohorts based on emerging safety findings.

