UX053 will be administered as an intravenous (IV) infusion over the course of at least 4 hours, with a slower rate of infusion for the first hour to minimize the risk of hypersensitivity or anaphylactoid-type reactions (refer to the Pharmacy Manual for additional infusion details) ([Table 3](#) and [Section 9](#)). The infusion rate may be slowed to minimize the risk of IRRs in individual subjects.

Premedication and Rescue Medication

All subjects, including those treated with placebo, will receive premedication at least 1 hour prior to the infusion, consisting of oral paracetamol/acetaminophen (500 mg) or ibuprofen (400 to 800 mg), an H2 blocker (eg, famotidine 20 mg or equivalent dose of another H2 blocker), and an H1 blocker (eg, cetirizine 10 mg or equivalent dose of another H1 blocker). For the premedication, paracetamol/acetaminophen is preferred over ibuprofen.

At the discretion of the Investigator, with input from Ultragenyx and the DMC, and based on the emerging safety profile of UX053, additional premedications and rescue medications may be used to reduce the risk and severity of immune reactions in RD cohorts. Premedication and rescue medication selection will be based on the nature of the reactions being observed and the risks of such medications in patients with GSD III.

If a subject develops an IRR that meets diagnostic criteria for anaphylaxis ([Section 8.3.3](#)), epinephrine should be administered as initial rescue medication. For all other hypersensitivity reactions \geq Grade 2 in severity suspected to be due to immune activation, dexamethasone should be the initial rescue medication. The Medical Monitor must be notified if any rescue medication is used.

If dexamethasone (or equivalent) is used as a rescue medication, premedication with dexamethasone (or equivalent) should be considered for that subject's subsequent infusions after discussion with the Medical Monitor.

[Section 8.3.2](#) provides subject-level redosing criteria, stopping criteria, and additional instructions on how to proceed in the event of an IRR.

Subjects will have cardiorespiratory monitoring throughout the infusions and will stay overnight for visits in which they receive study drug and be observed in an inpatient or observational unit for 24 hours after the end of each infusion. Prior to discharge, all the following criteria must be met:

- All scheduled study assessments have been completed.

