7.1.4. Dose Rationale

The planned doses of UX053 (0.05, 0.10, and 0.20 mg/kg) aim to establish a safe dose of UX053 in adults with GSD III, as well as provide a preliminary PK and PD profile of UX053. These doses were chosen based on single-dose and repeat-dose pharmacology studies in mouse and dog models of GSD III, and RD toxicology and toxicokinetic studies in rats, cynomolgus monkeys, and Beagle dogs. The NOAEL in repeat-dose studies with 5 total doses of UX053 administered Q2W was **CCI** mg/kg in dogs, **CCI** mg/kg in rats, and **CCI** mg/kg in monkeys. The maximum tolerated dose (MTD) was **CCI** mg/kg in rats and **CCI** mg/kg in monkeys. The MTD in dogs is not known since higher doses were not evaluated with Q2W administration. The MTD in dogs with weekly dosing of UX053 is **CCI** mg/kg, but this short interval between doses is believed to promote an accumulation of toxicity that does not occur with Q2W dosing. Hence, the MTD in dogs may be greater than **CCI** mg/kg when UX053 is administered Q2W, but remains undetermined. **CCI**

Taken together, these PK and drug metabolism properties of the drug support 1:1 weight-based scaling from nonclinical species to humans, which is an approach endorsed by a cross-industry consortium of experts in oligonucleotide therapies, the Oligonucleotide Safety Working Group (Kornbrust, 2019; Marlowe et al., 2017). The FIH starting dose of 0.05 mg/kg is **CCI** less than the NOAEL in the most sensitive nonclinical species, the dog. The highest potential FIH dose of 0.30 mg/kg is **CCI** less than the dog NOAEL. Additional details regarding the use of weight-based scaling versus body-surface area scaling, as well as summaries of nonclinical studies with UX053 are available in the IB.

Sequential dosing with an interval of 72 hours between subjects' first dose within a cohort and a 2-week minimum review of data between cohorts was chosen to allow enough time to detect any potential TEAEs, including potential immune responses. In nonclinical studies, toxicities generally occurred soon after dosing and promptly resolved. The DB-RD cohorts will aim to achieve a steady state with Q2W dosing. The OL-RD cohorts will aim to evaluate a Q4W dosing regimen. Subjects will receive premedication prior to the treatment infusion to prevent hypersensitivity reactions, in line with previously established programs evaluating RNA therapeutics.

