10.1.5. Safety Laboratory Tests

Blood and urine samples will be collected for safety laboratory tests as specified in [Table 4](#), [Table 5](#), and [Table 6](#). Fasting is not required. For visits in which subjects are receiving study drug, laboratory samples will be collected prior to dosing. All efforts should be made for urine collections to be from the first morning void. Samples will be processed by a central lab to ensure consistency across study sites.

In addition to chemistry, hematology, and urinalysis, additional assessments to monitor safety include activation of the complement pathway, coagulation factors, and interleukin-6. As noted in [Table 4](#), [Table 5](#), and [Table 6](#), samples for complement pathway, coagulation factors, and interleukin-6 are collected pre- and post-infusion. Post-infusion blood samples should be collected in the opposite arm of the infusion to avoid laboratory artefacts. The full list of safety laboratory evaluations to be performed in this study are listed in [Appendix 3](#). All laboratory samples listed in [Appendix 3](#) will be processed by a central laboratory, except urine pregnancy.

The study site should indicate to laboratories if the subject is taking high dose biotin supplements (found in multivitamins, biotin supplements, and some supplements to promote hair, skin, and nail growth) to potential risk of assay interference (eg, troponin) ([FDA, 2019a](#)).

The Investigator (and/or Medical Monitor) may at his/her discretion perform additional laboratory tests for subject safety if a subject experiences an SAE or other AE that may warrant further follow up.

Close monitoring is required for subjects who develop elevations in ALT > 3x ULN and > 2x their baseline value, or elevation in ALT > 3x ULN with INR > 1.5. This includes repeating liver enzymes and INR within 48 hours and consideration of additional diagnostic tests such as liver ultrasound.

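### Repeat-dose cohorts have no scheduled chemistry, hematology or PT/INR between the pre-dose sample and about Day 7, so a transient, symptom-free laboratory change could go unrecorded

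*Protocol*

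**What the plan says.** Protocol Section 5.5 (Risk Minimization) lists the safety laboratory times as before dosing in all cohorts and "again approximately 24 hours after dosing and at Day 4 (SAD cohorts) and Day 7 (both SAD and RD cohorts"). The bracket naming the SAD cohorts can be attached to Day 4 alone, or to both the 24-hour and the Day 4 sample.

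The schedules are clearer. Table 4 (SAD) has chemistry and hematology on D1, D4 and D7, and PT/INR on D1 and D7. Tables 5 (open-label, OL-RD) and 6 (double-blind, DB-RD) have no column between a dosing visit and the home visit one week later. For DB-RD the note to Table 6 reads "Gray columns indicate visits conducted at home (NOV, W1, W3, W5, W7, W9, W12, W24, and W36"). Footnote d of both tables makes the dosing-day samples pre-dose, and Section 10.1.5 agrees: "For visits in which subjects are receiving study drug, laboratory samples will be collected prior to dosing".

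Blood is drawn at 24 hours in the RD cohorts, but for PK only. Table 6 footnote f says "PK samples are also collected 24-hours post infusion", and Table 8 places this after the Week 0 infusion and after the Week 8 (DB-RD) or Week 12 (OL-RD) infusion. Under Section 7.1 subjects are to "be observed in an inpatient or observational unit for 24 hours after the end of each infusion".

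On when toxicity appears, Section 7.1.4 says that in nonclinical studies "toxicities generally occurred soon after dosing and promptly resolved".

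**The concern.** If toxicity tends to come early and clear promptly, a first look at about Day 7 is late. The tests that are absent in the interval are the ones by which Section 5.4.1 says liver injury would be evident (transaminases) and part of the panel for consumptive coagulopathy (PT/INR). The same analytes drive the redosing rules in Section 8.3.2 and several study stopping criteria in Section 8.3.3.

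An asymptomatic excursion that no scheduled sample catches cannot be judged clinically significant and entered as an adverse event. It would then be absent from the TEAE data, from the DMC's reviews before the next repeat-dose level, and from any laboratory-based criterion assessed on scheduled samples. The contrast with SAD adds to this: Section 7.1 has SAD subjects dosed one after another with review of 24-hour safety laboratory data in between, while subjects within an RD cohort can be dosed simultaneously.

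**Working it through.** The plan gives no figure for what its laboratory schedule would miss, so there is none to reproduce. The check is a reading of the schedules, followed by an illustration on stated assumptions.

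**Step 1: scheduled samples after a dose (Tables 4, 5, 6 and 8).**

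| | SAD | RD, each infusion |
|---|---|---|
| End of infusion | complement, IL-6, fibrinogen, d-dimer | the same |
| 24 hours | chemistry, hematology, PT/INR, PK | PK only, first and last infusion |
| Day 4 | chemistry, hematology (no PT/INR) | none |
| About Day 7 | chemistry, hematology, PT/INR | chemistry, hematology, PT/INR |

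Scheduled post-dose samples on Days 1 to 6 are therefore 2 for SAD chemistry and hematology, 1 for SAD PT/INR, and 0 for all three after each of the 5 DB-RD and 4 OL-RD doses.

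**Step 2: length of the gap.** It is nominally 7 days. Week 1 has a window of ±1 day, so the gap after Week 0 is 7 − 1 = 6 to 7 + 1 = 8 days. Later visits have ±2 days around targets set from baseline, so a dose at Week 2 and a sample at Week 3 can be 7 − 4 = 3 to 7 + 4 = 11 days apart.

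**Step 3: which reading of Section 5.5 was meant.** The protocol's summary of changes says "Text regarding the collection of safety labs in Section 5.5 Risk Minimization was updated to align with the schedule of events". That is evidence of intent only. Since the tables have no 24-hour RD sample, it favours reading the 24-hour sample as SAD only. On the other reading, Section 5.5 promises an RD sample that Tables 5 and 6 omit.

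**Step 4: what might remain at Day 7.** Assume a laboratory change peaks at 24 hours and declines with half-life h days. Six days separate the peak from Day 7, so the share of the peak remaining is 2^(−6/h):

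- h = 1: 2^(−6) = 0.016, about 2%
- h = 2: 2^(−3) = 0.125, about 13%
- h = 3: 2^(−2) = 0.25, or 25%
- h = 5: 2^(−1.2) = 0.435, about 44%

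Neither the peak time nor the half-lives come from the documents. A fast change would be almost gone and a slow one still partly visible.

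**Step 5: is the subject still in the unit at 24 hours?** Table 8 counts from the start of infusion, so the draw falls at 24 ± 2 hours. The infusion lasts at least 4 hours and observation runs 24 hours after it ends, so the stay lasts at least 4 + 24 = 28 hours from the start. The draw is inside the stay.

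**The case against.** The case for the schedule is substantial, and it rules out several stronger readings that a reader might reach.

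- **That the unmeasured toxicity grows with repeat dosing.** Section 5.4.1.1 reports "progressively higher magnitude induction of cytokines and complement activation at later doses in dogs and monkeys". That concerns cytokines and complement, which RD cohorts have sampled at the end of every infusion, with fibrinogen and d-dimer. The same section suggests that immune activation is partly upstream of liver and coagulation injury, so a link to ALT or INR can be inferred, but it is not stated.
- **That repeat-dose toxicity peaks and clears within a week.** Section 5.5 ties prompt onset to single doses. Its statement of when repeat-dose toxicity appeared is redacted. Section 5.4.1.1 calls transaminase rises transient only at lower doses and gives no duration.
- **That acute events are never recorded or cannot meet a stopping criterion.** Subjects are observed for 24 hours with vital signs to 24 hours, adverse events are collected at every visit, Section 10.1.5 allows extra tests after an adverse event, and the criteria in Section 8.3.3 apply throughout the study. The gap concerns scheduled samples and symptom-free changes.
- **That the primary safety data miss the toxicity.** The primary endpoint is TEAEs. Laboratory values become adverse events only when judged clinically significant.

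There are also safeguards before and between doses. Single-dose safety is evaluated before repeat dosing at the same level, OL-RD subjects receive no more than their own SAD dose, and a Day 7 sample precedes each next dose. The amendment history shows that the Week 3, 5 and 7 home visits with laboratory tests were added on regulators' recommendation, so the schedule was considered.

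All of this narrows the point. None of it supplies ALT, bilirubin, platelets or INR between the pre-dose sample and about Day 7 in a subject who feels well.

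**Conclusion.** The gap is real and limited. In the RD cohorts as designed, a transient, asymptomatic change in ALT, bilirubin, platelets or INR that resolves before about Day 7 would leave no trace in scheduled samples. It could then not reach the TEAE data, the DMC or the laboratory-based criteria by that route. Section 5.5 must also be reconciled with Tables 5 and 6.

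The size of the loss is unknown. The 2% to 44% range rests entirely on an assumed 24-hour peak and assumed half-lives of 1 to 5 days.

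A reader might infer that the trial's report will make repeat dosing look safer than it is. The documents do not support that. SAP Section 8 says the study ended after 4 subjects in each of cohorts 1S and 2S, and that only analyses specific to those cohorts will be provided. The point concerns the repeat-dose design as written, and any later study that reuses this schedule. It is a worthwhile, inexpensive improvement.

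**What to change.** Two changes:

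1. Reword Section 5.5 so that it states which cohorts have the 24-hour safety sample, and make Tables 5 and 6 agree with it.
2. Add chemistry, hematology and PT/INR tubes to the 24-hour PK draw already scheduled after the first and last RD infusions (DB-RD Weeks 0 and 8; OL-RD Weeks 0 and 12). If the extra blood is acceptable, take the same tubes at discharge after the other infusions. Show these time points in Tables 5 and 6.

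The cost is slightly more blood, more central-laboratory work, and a footnote in two tables. No extra visit is needed. Because Section 10.1.5 sends samples to a central laboratory, the documents do not show that results would be back before discharge. The gain is in what is recorded and later reviewed. The change adds a measurement and alters no dose, rescue or stopping rule.
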